9.3.1.2 Secondary outcome

Management and treatment during follow-up period

The management and treatment of interest are shown in **Table 2**.

9.3.2 Covariates

The following information will be extracted from MDV in this study.

Table 2. Definition of variables

Variable	Data extraction period	Details
Sex	Index date	Male/Female
Age	Index date	Age at Index date
Comorbidity and medical history	12 months before the index date (included)	
 - Coronary heart disease - Gastro-esophageal reflux disease - Obstructive sleep apnoea syndrome - Chronic obstructive pulmonary disease (COPD) - Lung cancer - Pulmonary hypertension 
See Annex 4 for code to define each comorbidity and medical history

Underlying disease (Pre-specified ILD)	12 months before the index date (included)	
 - Underlying Autoimmune Disease (Autoimmune ILD, Non-autoimmune ILD, Multiple, Unknown) - ILD Category (Hypersensitive pneumonitis, Exposure-related ILD, idiopathic nonspecific interstitial pneumonia (iNSIP), Unclassifiable idiopathic interstitial pneumonias (IIP), Sarcoidosis, RA-ILD, SSc-ILD, mixed connective tissue disease-ILD (MCTD-ILD), Other autoimmune ILD, Other ILD, Multiple, Unknown) - Pre-Specified ILD Clinical Diagnosis (Hypersensitive pneumonitis, Exposure-related ILD, iNSIP, Unclassifiable IIP, Sarcoidosis, RA-ILD, SSc-ILD, MCTD-ILD, Systemic Lupus Erythematosus-ILD (SLE-ILD), Polymyositis/Dermatomyositis-ILD (PM/DM-ILD), Sjogren ILD, Other autoimmune ILD, Other ILD, Multiple, Unknown) 
See Annex 5 for algorithm to define underlying diseases

Treatment	6 months before the index date (included) Follow-up period	
 - Rituximab - Tacrolimus - Mycophenolate - Cyclosporine - Cyclophosphamide - Azathioprine - Oral Corticosteroid - Tocilizumab - Nintedanib 
See Annex 3 for code to define each treatment
 
As for corticosteroid and immunosuppressive drugs during follow-up period, the same condition used for criteria of progression to PF-ILD will be applied.

Management	Follow-up period	
 - Oxygen therapy (HOT) - Lung transplant - Palliative care (oxygen inhalation, opioid use) 
See Annex 3 for code to define each management

Clinical examination	6 months before the index date (included)	
 - Pulmonary function test - HRCT/CT - KL-6 - SP-D 
See Annex 3 for code to define each clinical examination

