9.2.2 Study population

9.2.2.1 Eligibility criteria

Patients who meet all of the inclusion criteria and do not meet any of the exclusion criteria will be included in the study population.

Inclusion Criteria:

- 1) Patients diagnosed with at least two fibrosing ILD codes^{*1} on different dates in the patient identification period from 01-Jan-2013 to 6 months before 28-May-2020
- 2) Patients aged 18 years and older on the index date
- 3) Patients for whom data for the 12 months prior to the index date can be extracted as baseline data

*1 International Statistical Classification of Diseases and Related Health Problems (ICD-10) code or disease code: J84.1, J84.9, 8844510, 8848382, 8844341, 8848278, 8836513, 8848267, 8848302, 8839362, 8848283, 8837013, 8834158, 8848245, 8840951, 8847737

Exclusion Criteria:

- 1) Patients grouped into the underlying disease of IPF^{*1}
- 2) Patients who have met PF-ILD progression criteria during the baseline period

*1 Please refer to the ANNEX 5 for algorithm to define underlying diseases

Note: only diagnosis records without 'suspect flag' are to be considered for evaluating diagnosis related in/excl criteria"

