9.3 VARIABLES

9.3.1 Outcomes

9.3.1.1 Primary outcome

Incidence probability of progression to PF-ILDs at 6, 12, 18, and 24 months after the index date*

Progression to PF-ILD as event in this study is defined in Table 1 as well as Annex 2. Event date will be the date when the one of criteria of the progression to PF-ILD is met.

*The index date will be the date of the second diagnosis of fibrosing ILD. Please refer to the Section 9.2.2.1 for the detailed codes of fibrosing ILD.

Table 1. Interstitial lung disease progression proxies

Proxy
- ≥ 3 pulmonary function tests on different dates of service within 365 days - The date of the 3 rd pulmonary function test will be the date of progression
- ≥ 3 HRCT/CT on different dates of service within 365 days - The date of the 3 rd HRCT/CT will be the date of progression
≥ 1 claim for oxygen therapy (HOT) during follow-up period
≥ 1 respiratory hospitalization during follow-up period
≥ 1 claim for palliative care during follow-up period
≥ 1 lung transplant during follow-up period
≥ 1 new* claim for immunosuppressive drugs during follow-up period with at least two out of the three test codes** within 3 months before new claims for immunosuppressive drugs Rituximab Tacrolimus Mycophenolate Cyclosporine Cyclophosphamide Azathioprine Tocilizumab
*: Not received in the 12 months prior to the index date **: ① Pulmonary function tests, ② HRCT/CT, ③ KL-6 or SP-D
≥ 1 new* claim for oral corticosteroid with a prednisone-equivalent dose of >20 mg during follow-up period and with at least two out of the three test codes* within 3 months before new claims for oral corticosteroid *: Not received in the 12 months prior to the index date **: ① Pulmonary function tests, ② HRCT/CT, ③ KL-6 or SP-D
≥ 1 claim for Nintedanib* during follow-up period *: Patients meeting this criterion will be counted only if patients with fibrosing ILDs meet this criterion on or after 29-May-2020, because nintedanib was approved for PF-ILD on 29-May-2020. Even if patients with fibrosing ILDs meet this criterion on or before 28-May-2020, they will not be counted.

HRCT; high-resolution computed tomography, CT; computed tomography, KL-6; krebs von den lungen-6, SP-D; surfactant protein D

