9.7.2 Statistical analysis

9.7.2.1 Patient background characteristics and treatment

- Patient demographics (sex, age at the index date)
- Comorbidity and medical history during 12 months prior to the index date (included)
- Clinical examination, management, and treatment during 6 months prior to the index date (included)
- Duration of follow-up period, which is defined as “end of follow-up period” – “start of follow-up period” + 1 day
- Underlying diseases

These will also be analysed in patients with progression to PF-ILD and those without progression to PF-ILD respectively.

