9.7.2.3 Secondary outcomes

- Management and treatment during follow-up period

Frequency of patients with management and treatment during follow-up period will be analyzed.

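### Baseline treatment is tabulated over 6 months but new use is judged over 12, so for eight drugs a patient last treated 6 to 12 months before index who restarts appears in neither treatment row

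*Combined protocol and SAP*

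**What the plan says.** Three rules bear on whether a patient is shown as treated.

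- **Baseline treatment.** The Treatment row of Table 2 (section 9.3.2) has the extraction periods "6 months before the index date (included) Follow-up period". Section 9.7.2.1 agrees and lists "Clinical examination, management, and treatment during 6 months prior to the index date (included").
- **New use.** In Table 1 (section 9.3.1.1) the immunosuppressant and oral corticosteroid proxies require a new claim, with the footnote "Not received in the 12 months prior to the index date". Both also require two of three kinds of test in the preceding 3 months. The corticosteroid proxy has a dose threshold as well.
- **Follow-up treatment.** Table 2 adds: "As for corticosteroid and immunosuppressive drugs during follow-up period, the same condition used for criteria of progression to PF-ILD will be applied". These rows feed the secondary outcome in section 9.7.2.3: "Frequency of patients with management and treatment during follow-up period will be analyzed".

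Inclusion criterion 3 (section 9.2.2.1) admits only "Patients for whom data for the 12 months prior to the index date can be extracted as baseline data", so months 6 to 12 before index are available for everyone. No section explains why treatment is tabulated over 6 months when newness is judged over 12.

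**The concern.** The two windows leave a band between 6 and 12 months before index. Use in that band is too old for the baseline row but recent enough to stop a later claim for the same drug from being new. Because Table 2 applies the progression condition to the follow-up rows, that later claim drops out of the follow-up row too. Such a patient had the drug both before and after index and is shown with it at neither time.

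Two things are at stake. Treatment is the study's secondary objective, and its follow-up rows omit these restarts. In addition, the background table is reported overall, by progression status (section 9.7.2.1) and in three subgroup sets (section 9.7.3). A reader would naturally use it to see who could trigger a drug-start proxy, but it covers only half of the period that decides this.

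**Working it through.** The plan states no figure on this point, so the check is to apply its rules to each possible timing of last use.

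Inputs:
- baseline row: last pre-index claim at 6 months or less (Table 2, section 9.7.2.1);
- new: no receipt in the 12 months before index (Table 1);
- follow-up row: restart of the same drug that is also new (Table 2), taking the test and dose conditions as met so that only the windows are examined.

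| Last pre-index claim for the drug | Baseline row | Follow-up row after restart |
|---|---|---|
| 1, 5 or 6 months | yes | no |
| 7, 9 or 12 months | no | no |
| 13 months, or never | no | yes |

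The set in neither row is last use more than 6 and up to 12 months before index.

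**Drugs covered.** The seven immunosuppressants plus oral corticosteroid make 7 + 1 = 8 of the nine drugs in the Treatment row. The ninth is outside the gap: its proxy, "≥ 1 claim for Nintedanib* during follow-up period", carries a calendar-date rule but no newness rule, and the Table 2 sentence names only corticosteroid and immunosuppressive drugs.

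**Could exclusion criterion 2 empty the set?** It removes "Patients who have met PF-ILD progression criteria during the baseline period". That is not the same as prior drug use: a claim without the required tests does not meet a drug proxy, and the drug proxies are written for follow-up and relative to index. Some of these patients may be excluded, but the text does not exclude them all.

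**Size.** The documents hold no data on treatment intervals. As an assumption only, let a be the share of patients last treated with a drug in the 6-to-12-month band and r the share of those who restart it. Patients in neither row per 1,000 = 1,000 × a × r:
- low: 1,000 × 0.02 × 0.25 = 5;
- middle: 1,000 × 0.05 × 0.50 = 25;
- high: 1,000 × 0.10 × 0.75 = 75.

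**Which changes close the gap?** Re-applying the rules, each of these empties the set:
- *12-month baseline window:* the patients appear at baseline, but their restart is still not counted in follow-up.
- *6-month washout for new:* this would also change the definition of the primary event.
- *Follow-up row counting any claim:* the restart is counted, and the primary event is untouched.

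**The case against.** The strongest reply is that the windows answer different questions. Twelve months is a washout for new use; six months describes recent treatment, and Table 2 uses the same six months for clinical examinations. Nothing says that the baseline and follow-up rows must add up to all treated patients. This stands: a reader might infer that the plan contradicts itself, and it does not. Nor does a row labelled as six months declare anyone drug-naive. What remains is that no table shows the restart, or the 12-month prior use that governs eligibility for the drug-start proxies.

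A second reply is that the Table 2 sentence loses more treatment than the windows do. A never-treated patient who starts one of these drugs without the required tests, or a corticosteroid at or below the threshold, is also in neither row. Patients treated within 6 months who continue are missing from follow-up, though they do appear at baseline. This stands too, and it is why widening the baseline window cannot be the whole repair.

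Other stronger readings go beyond the text:

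- *That the primary estimate is biased by the 6-month window.* That window does not enter the Kaplan-Meier analysis in section 9.7.2.2.
- *That a 12-month column would divide patients cleanly into those eligible and ineligible for a drug proxy.* Table 2 includes the index date, whereas the Table 1 washout is worded as prior to it. The plan does not say whether new is judged per drug or per class, or whether earlier corticosteroid use counts at any dose.
- *That prior use of one drug type bars both drug proxies.* Prior corticosteroid use does not bar the immunosuppressant proxy, or the reverse.
- *That the loss can be quantified.* Any share of prior users missed by the 6-month window only restates what is assumed about claim spacing, and it counts all users in the band, not the smaller group who restart.

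**Conclusion.** The point holds in a limited form. For eight of nine drugs, a patient whose last use was more than 6 and up to 12 months before index and who restarts the same drug is in neither the baseline nor the follow-up treatment row. The baseline table also does not show how many patients were ineligible for each drug-start proxy. The effect is confined to the descriptive baseline tables and the secondary outcome.

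The size is unknown; 5 to 75 per 1,000 rests wholly on the assumed ranges above. Attributing the lost restart to the washout also assumes that the test and dose conditions were met, since otherwise the follow-up row would omit it anyway. This is a cheap improvement to reporting rather than a flaw in the primary analysis.

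**What to change.** 1. In Table 2 (Treatment) and section 9.7.2.1, add a baseline treatment column for the 12 months prior to the index date, with the same window boundary as the Table 1 washout. Keep the 6-month column and label it recent treatment.
2. In Table 2 and section 9.7.2.3, add follow-up rows that count any claim for each drug, beside the rows restricted to the progression condition. Without this, the restart stays out of the secondary outcome.
3. So that the new column can be read as ineligibility for each proxy, state whether new is judged per drug or per class and whether prior corticosteroid use is judged at any dose.

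The data are already required by inclusion criterion 3, and the primary event definition can stay as it is. The cost is a few extra descriptive rows and a re-run of those tables. The 12-month column will include some drugs no longer in use at index, which the 6-month column beside it helps to show.

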8.2 SECONDARY OBJECTIVE

To investigate the characteristics of procedures for management and treatment in patients with fibrosing ILD other than IPF in real-world setting in Japan

[figure not shown]

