9.7 DATA ANALYSIS

9.7.1 Common handling for statistical analysis

Unless otherwise specified, descriptive analysis is planned.

The summary statistics for continuous variables are N, mean, standard deviation, minimum, 25th percentile (Q1), median, 75th percentile (Q3), and maximum.

Tabulations of frequencies for categorical variables will include all possible categories and will display the number of observations in a category as well as percentage (%) relative to the population analysed. The precision for percentage will be one decimal point.

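### Table 2 counts follow-up immunosuppressant and oral corticosteroid use only when it meets the progression condition, so 8 of 12 secondary-outcome items do not describe treatment in the cohort

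*Combined protocol and SAP*

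**What the plan says.** Section 8.2 sets the secondary objective: "To investigate the characteristics of procedures for management and treatment in patients with fibrosing ILD other than IPF in real-world setting in Japan". Section 9.3.1.2 takes the items from Table 2 ("The management and treatment of interest are shown in" that table), and Section 9.7.2.3 plans the frequency of patients with each item during follow-up.

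Under Treatment, Table 2 in Section 9.3.2 adds: "As for corticosteroid and immunosuppressive drugs during follow-up period, the same condition used for criteria of progression to PF-ILD will be applied". The condition is in Table 1 (Section 9.3.1.1) and is repeated in Annex 2. It has these parts:

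- The claim must be new, defined as "Not received in the 12 months prior to the index date".
- For immunosuppressants it must come "with at least two out of the three test codes within 3 months before new claims for immunosuppressive drugs". The three test types are pulmonary function tests, HRCT/CT, and KL-6 or SP-D.
- For corticosteroid the same test requirement applies, and the criterion is a new "claim for oral corticosteroid with a prednisone-equivalent dose of >20 mg during follow-up period".

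Section 9.7.1 gives each frequency as a "percentage (%) relative to the population analysed". Annex 3 lists the codes for the same drugs without any such condition.

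**The concern.** A reader of the abstract or Section 9.7.2.3 will take the reported percentage for, say, tacrolimus as the share of the cohort treated with it during follow-up. Under the Table 2 sentence it is the share with a follow-up claim that also counts as a progression proxy. Section 7 gives as a reason for the study that current management and treatment in Japan are not well known, and for these eight drugs the planned rows would not supply that information.

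Nothing else in the plan does. The baseline treatment table has no such condition, but it covers the 6 months up to index, not follow-up. The sensitivity analyses in Section 9.7.4 change the data cut-off and the index date. The optional analysis with modified progression criteria is not a commitment to an unrestricted count. Section 9.9 explains possible underestimation of frequency only by care given outside the database hospitals. The restricted definition is also carried into every subgroup in Section 9.7.3.

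**Working it through.** The plan states no expected frequency or precision target for these items, so there is no planned figure to reproduce. The check traces the definitions.

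**1. Items affected.** Table 2 lists 9 drugs and 3 management items with a follow-up period: 9 + 3 = 12. The sentence covers the 7 immunosuppressants and oral corticosteroid: 7 + 1 = 8. Nintedanib, home oxygen, lung transplant and palliative care fall outside it.

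**2. Who is not counted.** Applying the Table 1 condition to the Table 2 rows leaves out:

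- patients with no follow-up claim preceded by two of the three test types within 3 months;
- corticosteroid users who never meet the dose limb;
- on the plain reading of *new*, patients who received the drug in the 12 months before index, including those who simply continue it.

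The third group can be in the cohort. Exclusion criterion 2 removes patients who met the progression criteria in baseline, not prior users of these drugs as such, and the plan itself tabulates their use before index.

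**3. Patients without progression.** Section 9.3.1.1 makes meeting any one criterion the event. A patient counted in one of the eight rows has met a criterion in follow-up and is therefore a progressor. It follows that

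- number of patients without progression counted for any of the eight drugs = 0, whatever they actually received;
- these patients remain in the denominator, because percentages refer to the population analysed.

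**4. Baseline against follow-up.** Baseline rows are unconditional over 6 months; follow-up rows are conditional, with a 12-month lookback. The two are not comparable for the same drug. On the plain reading, a patient whose only receipt before index fell in months 7 to 12 before it and who takes the drug again in follow-up appears in neither.

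**5. Illustration with assumed inputs.** None of these shares is in the documents. Let

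- p = share of a drug's follow-up users who received it in the 12 months before index, assumed 25% to 75%;
- t = share of the remaining users with a claim that meets the test requirement, assumed 30% to 90%;
- d = for corticosteroid, share of those who also meet the dose limb, assumed 30% to 60%.

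Fraction counted = (1 − p) × t, multiplied by d for corticosteroid.

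- Immunosuppressants, low: 0.25 × 0.30 = 0.075. High: 0.75 × 0.90 = 0.675.
- Corticosteroid, low: 0.075 × 0.30 = 0.0225. High: 0.675 × 0.60 = 0.405.

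If 40% of the cohort truly used an immunosuppressant, the row would show between 0.40 × 0.075 = 3.0% and 0.40 × 0.675 = 27.0%. The width of that range reflects the assumptions and is not an estimate of the undercount.

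**The case against.** The rule is explicit and pre-specified, and Section 9.3.1.2 sends the reader to the table that contains it. It may be deliberate: any-claim counts would include drugs given for extrapulmonary autoimmune disease, and requiring recent lung tests could limit that. The outcome is secondary and descriptive, with no hypothesis test. An abstract that omits an operational detail is not a contradiction. All of this is fair, although the documents do not state that rationale. It argues for keeping the qualified count and labelling it. It does not turn that count into a description of treatment in the cohort.

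A reader might go further in four ways that the documents do not support:

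- *Anyone who starts without two test types is lost.* Not so. *New* is anchored to the index date, not to the start of the drug. For a patient with no receipt in the 12 months before index, a later follow-up claim preceded by two test types can still qualify.
- *The rows merely repeat the per-criterion breakdown in Section 9.7.2.2.* That breakdown is among progressors, and Table 1 has one criterion for all seven immunosuppressants, whereas Table 2 lists them singly. Only the corticosteroid row is close to a repeat.
- *Most users are missed.* No document figure supports any size.
- *Uncertainty over what counts as new belongs to this point.* Whether it is judged per drug or per class, and whether non-receipt of corticosteroid means any receipt or receipt above the dose limb, is an ambiguity in Table 1 that also bears on the primary event. It should be raised separately.

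**Conclusion.** The point holds. For 8 of 12 follow-up treatment and management items, the secondary outcome reports progression-qualifying new treatment, and the objective in Section 8.2 is not answered for those drugs. The zero contribution from patients without progression follows from the definitions and needs no assumption. The loss of prior users rests on the plain reading of *new*. The direction is certain: the qualified count cannot exceed the any-claim count. The amount cannot be determined from the documents.

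The Table 2 sentence does not enter the Kaplan-Meier analysis, and changing it would leave the progression event as it stands. Resolving the separate Table 1 ambiguity could change that event.

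**What to change.** Change the Table 2 sentence so that the secondary outcome reports, for each of the eight drugs, the number and percentage of patients with any follow-up claim by the Annex 3 codes. Ideally, split this by whether that drug was claimed in the 12 months before index. Keep the progression-qualified count as a separate row, labelled as such. State in Section 9.9 that any-claim counts include use for extrapulmonary disease.

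No new data or code list is needed: Annex 3 already holds the codes, and inclusion criterion 3 requires 12 months of baseline data. The cost is one sentence in Table 2, one in Section 9.9, and output volume. Section 9.7.3 defines 4 + 12 + 15 = 31 strata, 32 with the overall cohort. The main analysis, two sensitivity analyses and their combination make 4 sets, so 32 × 4 = 128 tables. One extra row per drug adds up to 8 × 128 = 1,024 counts; with the split (any, prior claim, no prior claim), 8 × 3 × 128 = 3,072. The split could be confined to the overall cohort if that is too much. A 12-month lookback column in the baseline treatment table would help comparison but is optional.
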